3.3. Safety Monitoring

The function and composition of the SET is described in [Section 12.7](#). Upon completion of the first 2 cycles for all subjects in each dose cohort, there will be a review of all available safety data (at the time of decision-making) by the SET.

Decisions on DLT determination, dose escalations or de-escalations, changes in the timing of pharmacokinetic/ADA or pharmacodynamic sampling, exploration of alternative schedule(s), cycle duration, or other study conduct recommendations, will be made by the SET and documented in a SET decision document and distributed to investigators. The Institutional Review Board (IRB) will be notified before implementation of any SET decision, if required. This document will be provided in the sponsor's instruction manual and retained in the study master file and in the study center's files.

3.3.1. Evaluation of Dose-limiting Toxicity

Dose-limiting toxicities will be assessed during the first and second treatment cycle (ie, first 28 days of study therapy) starting with the first day of combination therapy (ibrutinib and nivolumab). Only AEs that occur during this time period, and after a subject has received at least one dose of nivolumab and one dose of ibrutinib, will be considered for DLT. Adverse events fulfilling the criteria of DLT need to be reviewed and confirmed by the SET. In addition, all AEs occurring while a subject is participating in the study will be reviewed by the SET as part of the continued safety evaluation ([Section 12.7](#)). All subjects in Part A will be evaluated for DLTs. Subjects who are not evaluable for DLT may be replaced; the safety profile of subjects who were replaced will be included in the SET review.

The following AEs considered to have at least a possible relationship to study therapy by the investigators and confirmed by the SET will qualify as DLTs:

- Any AE that requires discontinuation of study drug (see also Section 6.4.3, Table 8, and Table 9)
- Any AE that results in a delay of dosing for more than 2 weeks within the DLT period
- Central nervous system hemorrhage of any grade.

3.3.2. Dose Optimization – Part A

During the dose optimization stage, subjects will be entered in each dose level based on a modified Toxicity Probability Interval (mTPI) method (Ji and Wang 2013).³⁰ The size of the group can be changed as indicated by safety. A minimum of 6 and up to 9 subjects may be treated in each dose cohort.

After the last subject in each group has completed treatment in the DLT observation period, the SET will evaluate all safety and pharmacokinetic data and make the decision whether to escalate, stay at the current dose or de-escalate the dose cohort with the second group of subjects treated, based on the guidelines outlined in Attachment 1.

3.3.3. Dose Expansion - Part B (Recommended Phase 2 Dose)

The dose for the expansion part of this study (Part B) will be determined based on either:

- The highest planned dose (ibrutinib 560 mg daily + nivolumab 3 mg/kg every 2 weeks) in the dose optimization schedule
- A lower dose determined by the SET following a review of all available safety and efficacy data from the dose optimization part of the study (Part A)

4. SUBJECT POPULATION

Screening for eligible subjects will be performed within 28 days before administration of the study drug. The inclusion and exclusion criteria for enrolling subjects in this study are described in the following 2 subsections. If there is a question about the inclusion or exclusion criteria below, the investigator must consult with the appropriate sponsor representative and resolve any issues before enrolling a subject in the study. Waivers are not allowed.

For a discussion of the statistical considerations of subject selection, refer to Section 12.3, Sample Size Determination.

4.1. Inclusion Criteria

Each potential subject must satisfy all of the following criteria to be enrolled in the study. In addition, subjects enrolled to each cohort must satisfy cohort-specific criteria as listed below.

1. Subject must be 18 years of age or older.
2. Eastern Cooperative Oncology Group (ECOG) performance status grade 0, 1, or 2 ([Attachment 4](#))
3. Adequate bone marrow, liver, and renal function defined as:
 - Absolute neutrophil count (ANC) $\geq 1.5 \times 10^9$ cells/L (ie, $\geq 1500/\mu\text{L}$).
 - Platelets $\geq 75 \times 10^9$ cells/L (ie, $\geq 75,000/\mu\text{L}$) without transfusion support within 7 days prior to test.
 - Hemoglobin $\geq 8\text{g/dL}$ without transfusion support within 7 days prior to test
 - Alanine aminotransferase (ALT) and aspartate aminotransferase (AST) $\leq 2.5 \times$ upper limit of normal (ULN)
 - Total bilirubin $< 2\text{mg/dL}$ (unless due to Gilbert's syndrome).
 - Creatinine determined by serum creatinine levels $\leq 1.5 \times$ ULN or a calculated creatinine clearance of $\geq 50 \text{ mL/min/1.73 m}^2$ (see [Attachment 2](#) for Modified Diet in Renal Disease [MDRD] formula)
4. Women of childbearing potential (WOCBP) and men who are sexually active with a woman of childbearing potential must be practicing a highly effective method of birth control during and after the study, consistent with local regulations regarding the use of birth control methods for subjects participating in clinical studies. These restrictions apply for the duration of treatment with study drug plus 5 half-lives of study drug plus 30 days (duration of ovulatory cycle) for a total of 23 weeks post nivolumab treatment or 3 months post ibrutinib completion (whichever occurs last).
5. Men who are sexually active with WOCBP must agree to follow instructions for method(s) of contraception for the duration of treatment with study drug plus 5 half-lives of study drug plus 90 days (duration of sperm turnover) for a total of 31 weeks post nivolumab treatment or 12 weeks post ibrutinib completion (whichever occurs last).
6. Women of childbearing potential must have a negative serum or urine pregnancy test (minimum sensitivity 25 IU/L or equivalent units of HCG) within 24 hours prior to the start of study drug.

7. Men must agree to not donate sperm during or for a total of 31 weeks post nivolumab treatment or 3 months post ibrutinib completion (whichever occurs last) and a woman must agree not to donate eggs (ova, oocytes) for the purposes of assisted reproduction during or for a total of 23 weeks post nivolumab treatment or 3 months post ibrutinib completion (whichever occurs last).
8. Must sign (or their legally-acceptable representatives must sign) an informed consent document indicating that they understand the purpose of and procedures required for the study, including biomarkers, and are willing to participate in the study.
9. Subject is able to swallow capsules and is able to take or tolerate oral medications on a continuous basis.

4.1.1. Additional Inclusion Criteria for Part A: Dose Optimization Cohorts

10. Histologically confirmed and documented B-NHL (FL and DLBCL) or CLL/SLL (deletion 17p or deletion 11q as determined by FISH analysis) as conducted by the local lab.
11. Relapsed or refractory disease after at least 1 but not more than 4 lines of prior, systemic therapy.
12. Measurable disease defined as:
 - **B-NHL:** At least 1 measurable site of disease according to the Lugano Classification (see Attachment 6.2). The site of disease must be greater than 1.5 cm in the long axis regardless of short axis measurement or greater than 1.0 cm in the short axis regardless of long axis measurement, and clearly measurable in 2 perpendicular dimensions
 - **CLL:** $\geq 5,000$ leukemia cells/ μL

4.1.2. Additional Inclusion Criteria for Part B: Expansion Cohorts

Cohort B1: Chronic Lymphocytic Leukemia/or Small Lymphocytic Lymphoma

13. Criterion modified per amendment
 - 13.1 Diagnosis of CLL requires the following:
 - Lymphocytosis with $\geq 5,000$ B-lymphocytes/ μL .
 - Prolymphocytes $\leq 55\%$ of total blood lymphocytes.
14. Criterion modified per amendment
 - 14.1 Diagnosis of SLL requires measurable disease

15. Criterion modified per amendment

15.1 CLL/SLL with deletion of short arm of chromosome 17 ie, del(17p13.1) or deletion of the long arm of chromosome 11 ie, del(11q21-q23) as defined by del(17p) or del(11q) in $\geq 20\%$ of cells based on interphase FISH and documented in subject's record prior to start of study therapy.

16. Criterion modified per amendment

16.1 Relapsed or refractory CLL/SLL following at least 1 prior line of systemic therapy (consisting of at least 2 cycles of a chemotherapy containing regimen)

17. Active disease meeting at least 1 of the criteria outlined by the IWCLL ([Attachment 6.1](#)):

- Evidence of progressive marrow failure as manifested by the development of, or worsening of, anemia or thrombocytopenia
- Massive (ie, at least 6 cm below the left costal margin), progressive, or symptomatic splenomegaly
- Massive nodes (ie, at least 10 cm in longest diameter), progressive, or symptomatic lymphadenopathy
- Progressive lymphocytosis with an increase of more than 50% over a 2-month period or a lymphocyte doubling time (LDT) of less than 6 months (which may be extrapolated). Lymphocyte doubling time can be obtained by linear regression extrapolation of absolute lymphocyte count (ALC) obtained at intervals of 2 weeks over an observation period of 2 to 3 months. For patients with initial ALC of less than $30 \times 10^9/L$ ($30,000/\mu L$), LDT should not be used as a single parameter to define indication for treatment. In addition, factors contributing to lymphocytosis or lymphadenopathy other than CLL (eg, infections) should be excluded
- Constitutional symptoms, defined as 1 or more of the following disease-related symptoms or signs:
 - Unintentional weight loss of $>10\%$ within the previous 6 months prior to screening
 - Significant fatigue (inability to work or perform usual activities)
 - Fevers higher than $100.5^\circ F$ or $38.0^\circ C$ for 2 or more weeks without evidence of infection; or
 - Night sweats for more than 1 month without evidence of infection

Cohort B2: Follicular Lymphoma

18. Histologically confirmed initial diagnosis of FL of Grade 1, 2, or 3a according to World Health Organization (WHO) criteria without pathological evidence of transformation.
19. Relapsed or refractory disease defined as:
 - Previously treated with at least 2 prior lines of therapy using different treatment regimens and separated by disease progression or relapse
 - Received or not eligible for prior treatment with a CD20 antibody combination chemotherapy regimen
20. At least 1 measurable site of disease according to the Lugano Classification ([Attachment 6.2](#)).

Cohort B3: Diffuse Large B-cell Lymphoma

21. Histologically-confirmed DLBCL.
22. Previously treated with a standard, rituximab and anthracycline-containing systemic chemotherapy regimen (such as R-CHOP), or
Received or not eligible for high-dose chemotherapy and autologous stem cell transplantation (HD-ASCT)
Of Note: Additional, prior salvage chemotherapy regimens are allowed
23. At least 1 measurable site of disease based on the Revised Response Criteria for Malignant Lymphoma ([Attachment 6.2](#)).

Cohort B4: Richter Syndrome

24. Histologically-confirmed Richter syndrome defined as transformation of CLL or SLL into an aggressive lymphoma
25. Previously treated with at least one line of standard, systemic chemotherapy or not eligible for standard therapy
26. At least 1 measurable site of disease based on the Revised Response Criteria for Malignant Lymphoma ([Attachment 6.2](#)).

4.2. Exclusion Criteria

Any potential subject who meets any of the following criteria will be excluded from participating in the study.

1. Major surgery within 4 weeks of the first dose of ibrutinib.
2. Diagnosed or treated for malignancy other than the indication under study except for:
 - Malignancy treated with curative intent and with no known active disease present for ≥ 3 years before the first dose of ibrutinib or nivolumab
 - Adequately treated non-melanoma skin cancer or lentigo maligna without evidence of disease
 - Adequately treated cervical carcinoma in situ without evidence of disease
3. History of stroke or intracranial hemorrhage within 6 months prior to the first dose of ibrutinib.
4. Requires anticoagulation with warfarin or equivalent vitamin K antagonists (eg, phenprocoumon).
5. Requires treatment with strong CYP3A inhibitors ([Attachment 8](#)).
6. Criterion modified per amendment 1
 - 6.1 Clinically significant cardiovascular disease such as uncontrolled or symptomatic arrhythmias, congestive heart failure, or myocardial infarction within 6 months of Screening, or any Class 3 (moderate) or Class 4 (severe) cardiac disease as defined by the New York Heart Association Functional Classification ([Attachment 3](#)), or congenital long QT syndrome, or QT interval corrected for heart rate, using Fridericia formula²¹ (QTcF) at Screening >470 ms.
7.
 - Subjects with a history of Human Immunodeficiency Virus (HIV)
 - Subjects who have active infection or are chronic carriers of Hepatitis B or Hepatitis C.
8. History of disallowed therapies:
 - Prior treatment/exposure with ibrutinib or other BTK inhibitor
 - Prior exposure to anti-PD1, anti-PDL1, anti-PD-L2, anti-CD137 or anti-cytotoxic T-lymphocyte associated antigen 4 (CTLA-4) antibody
 - Concurrent enrollment in another therapeutic investigational clinical study

9. Prior anti-tumor therapy including (all times measured prior to start of study therapy)
 - nitrosoureas within 6 weeks
 - chemotherapy within 3 weeks
 - therapeutic antibodies within 4 weeks
 - radio- or toxin-immunoconjugates within 10 weeks
 - radiation therapy within 3 weeks
 - investigational agents within 3 weeks
 - carmustine (BCNU) ≥ 1000 mg received as part of pre-transplant conditioning regimen
 - chest radiation ≤ 24 weeks prior to first dose of the study drug
10. Criterion revised per Amendment 4
 - 10.1 Known central nervous system (CNS) lymphoma.
11. Received an allogeneic hematopoietic SCT.
12. Any uncontrolled active systemic infection, active non-infectious pneumonitis, evidence or history of interstitial lung disease, or any life-threatening illness, medical condition, or organ system dysfunction which, in the investigator's opinion, could compromise the subject's safety, interfere with the absorption or metabolism of ibrutinib capsules, or put the study outcomes at undue risk.
13. Any active autoimmune disease or a documented history of autoimmune disease (excluded/exception to the rule: subjects with vitiligo or resolved childhood asthma/atopy, type I diabetes mellitus, subjects with hypothyroidisms stable on hormone replacement, Sjorgen's syndrome, psoriasis not requiring systemic treatment, or conditions not expected to recur in the absence of an external trigger).
14. Any syndrome that requires systemic treatment with either corticosteroids (> 10 mg daily prednisone equivalents) or other immunosuppressive medications within 14 days of study drug administration. Of note: Inhaled or topical steroids, and adrenal replacement doses > 10 mg daily prednisone equivalents, are permitted in the absence of active autoimmune disease.
15. A woman who is pregnant or breast feeding.
16. Subject is or has an immediate family member (spouse or children) who is investigational site or sponsor staff directly involved with this trial, unless prospective IRB approval (by chair or designee) is given allowing exception to this criterion for a specific subject.

NOTE: Investigators should ensure that all study enrollment criteria have been met at screening. If a subject's status changes (including laboratory results or receipt of additional medical records)

after screening but before the first dose of study drug is given such that he or she no longer meets all eligibility criteria, the subject may be re-evaluated at a later timepoint to assess eligibility.

4.3. Prohibitions and Restrictions

Potential subjects must be willing and able to adhere to the following prohibitions and restrictions during the course of the study to be eligible for participation:

1. Requires surgery or invasive procedures:
 - For any surgery or invasive procedure requiring sutures or staples for closure, ibrutinib and nivolumab should be held at least 7 days prior to the intervention and should be held at least 7 days after the procedure, and restarted at the discretion of the investigator when the surgical site is reasonably healed without serosanguineous drainage or the need for drainage tubes
 - For minor procedures (such as a central line placement, tissue or needle biopsy, thoracentesis, or paracentesis) ibrutinib and nivolumab should be held for at least 3 days prior to the procedure and should not be restarted for at least 3 days after the procedure. For bone marrow biopsies that are performed while the subject is on ibrutinib, it is not necessary to hold ibrutinib for these procedures
 - For emergency procedures, ibrutinib and nivolumab should be held after the procedure until the surgical site is reasonably healed, for at least 7 days after the urgent surgical procedure
2. Foods or beverages containing grapefruit or Seville oranges should be avoided, as these contain certain ingredients that inhibit CYP3A.
3. Prohibited medications and precautions with concomitant medications as detailed in Section 9.

5. TREATMENT ALLOCATION AND BLINDING

Randomization will not be used in this study. Subjects will be sequentially assigned to treatment. No blinding is required as this is an open-label study. All subjects enrolled will receive open-label treatment with ibrutinib capsules and nivolumab infusions.

6. DOSAGE AND ADMINISTRATION

6.1. Study Treatment Administration

For the purposes of this study, ‘study drug’ or ‘study therapy’ refers to both ibrutinib and/or nivolumab. All dosing information must be recorded in the Dosage Administration page of the eCRF. A treatment and study design scheme is provided in [Figure 1](#).

The duration of each treatment cycle is 14 days. Day 1 or start day of a new cycle is triggered by the infusion of nivolumab. The cycle duration may be changed based on decision by the SET (Section 3.3). Study drugs will be administered until disease progression or unacceptable toxicity,

whichever occurs first. On days when both drugs will be administered, the sequence of administration will be nivolumab IV followed by oral ibrutinib.

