| CT imaging (neck, chest, abdomen, and pelvis) with oral and IV contrast | CT scan with IV contrast (oral if IV is contraindicated) of the neck, chest, abdomen, and pelvis and any other disease sites present at Screening. MRI only for disease sites that cannot be adequately imaged using CT. Brain MRI required only if clinically indicated. | X (imaging part of standard assessments; within 6 weeks prior to dosing is acceptable) | | Q5cycles (starting cycle 5) for first 15 months, thereafter Q12 cycles until PD. After clinical cutoff, disease assessments to be performed Q12 cycles or per local standards (but at a minimum of Q26 weeks). To be performed at the time of atypical responses 'tumor flare'. The same imaging technique used at Screening should be used throughout the study. Results are preferably available before start of treatment in the following cycle. During Follow-up, to be performed at PD and at least Q6 months up to PD or start of subsequent therapy | |
| Whole body FDG-PET scan | For NHL assessments, PET scan at baseline is recommended but not mandatory. Maximal tumor reduction: eg CR or 2 consecutive CT scans showing no further tumor reduction. | X | | at the time of maximal tumor reduction, relapse from CR | |
| Evaluation of other sites of disease | May be performed by radiological imaging, physical examination, or other procedures as necessary | as clinically indicated | | as clinically indicated, using the same method of assessment as used at Screening | |

| | Notes | Screening Period | Treatment Period (14 day cycles) | | | Follow-up Period ^a |
|---|---|---|---|--------------------------|-----|-------------------------------|
| | | up to 28 days before start of any study treatment | BASELINE ASSESSMENT CID1 (without run-in phase) CID-7 (with run-in phase) | Day 1, subsequent cycles | EOT | Q3m |

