6.3. Nivolumab Administration

Eligible subjects will receive treatment with nivolumab at a dose of 3 mg/kg given as a 60-minute IV infusion on Day 1 of every 14-day cycle. If the subject's weight on the day of dosing differs by > 10% from the weight used to calculate the dose, the dose must be recalculated. All doses should be rounded to the nearest milligram.

There are no premedications recommended for nivolumab on the first cycle. If an acute infusion reaction is noted, subjects should be managed according to guidelines provided in Section 8.11.

Subjects may receive nivolumab infusions with no less than 12 days between doses and no more than 3 days after the scheduled dosing date. A dose given after the 3-day window is considered a dose delay. A maximum delay of 42 days between doses is allowed.

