6.4. Dose Modifications

Treatment modifications may be made to both ibrutinib and nivolumab. Changes in dose apply only to ibrutinib. Nivolumab will be given at fixed dose, treatment modifications are primarily dose delays.

Adjustments of study drug dose should be overseen by the principal- or sub-investigator(s) unless an immediate safety risk is apparent. The dose adjustments are applicable to all subsequent treatment cycles.

Note: The recommendation to discontinue study therapy applies to both study drugs. If appropriate and after consultation with the Sponsor, subjects may receive ibrutinib alone. Following implementation of amendment 7, treatment with single agent ibrutinib will be discontinued and an End of Trial visit will be performed for patients not scheduled to rollover into long-term extension study CAN3001. Patients scheduled to roll over into Study CAN3001 will continue treatment.

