Attachment 5: Efficacy procedures**Evaluations****Radiographic Image Assessments**

During the study, disease response will be assessed using CT scans with IV contrast of the neck, chest, abdomen, and pelvis and any other location where disease was present at Screening or whole body FDG-PET scans. Subjects who are intolerant of IV CT contrast agents will have CT scans performed with oral contrast. Endoscopy is required to confirm CR for subjects with gastrointestinal (GI) involvement at baseline.

A separate CT scan and PET scan are preferred but, if the only available modality is combined/dual PET/CT scanner, then the CT portion of a PET/CT may be submitted in lieu of a dedicated CT; however, the CT scanning must be done according to certain imaging requirements provided to the radiologist in the radiology manual to ensure that an optimized CT examination is done. Evaluation of other sites of disease by radiological imaging, physical examination, or other procedures as necessary (to be performed throughout the study using the same method of assessment used to assess disease at baseline), and review of hematology and clinical chemistry results may be performed at the site level, as determined by the investigator.

Magnetic resonance imaging may be used to evaluate sites of disease that cannot be adequately imaged using CT (in cases where MRI is desirable, the MRI must be obtained at baseline and at all subsequent response evaluations). For all other sites of disease, MRI studies do not replace the required neck, chest, abdomen, and pelvic CT scans. Brain MRI and lumbar puncture are required, only if clinically indicated.

Radiological assessments will be performed at Screening, every 5 cycles (starting Cycle 5) or approximately every 10 weeks up to 15 months after the start of study drug. Thereafter, scans will be performed every 12 cycles (approximately every 24 weeks) until disease progression, or death, or end of study, whichever comes first. A PET scan will be performed at Screening. For subjects who are PET-positive at baseline, PET scans will be done at the time of maximal tumor reduction (eg, CR or 2 consecutive CT scans showing no further tumor reduction), relapse from CR, and at suspected disease progression if new lesion was detected on CT.

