2.2. Visit Windows

Visit window will be based on phases and cycles:

(For the purposes of this study, ‘study drug’ or ‘study therapy’ or “study treatment” refers to both ibrutinib and/or nivolumab).

Screening: Up to 28 days before the start of any study treatment.

Treatment: Between the date of first administration of study therapy and the date of the last dose of study drug. The treatment stage will be subdivided by cycles. Each cycle is 14 days, starting from the first dose of study drug. The end date of the last cycle is the date of the last dose of study drug received during the study.

End of treatment: within 30 days after the last dose of ibrutinib or 100 days after the last nivolumab. The assessments performed during the ‘End of treatment visit’ will be included in this End of treatment phase.

Follow-up: After the end of treatment till the last assessment for the last subject in the study (e.g. the last follow-up visit or death).

Baseline assessment is defined as the last non-missing results on or before the first dose of study therapy.

1. Cycle-based analysis may be performed for safety parameters during the treatment up to date of last dose of ibrutinib + 30 days, and last dose of nivolumab +100 days. For the analysis of laboratory measurement by cycle, the mean values within each cycle will be used. For the analysis of laboratory grade by cycle, the worst grade within each cycle will be used.

Assessments will be presented chronologically by cycle day or study day, which are defined as the follows:

Day 1 = date of first dose of study drug / Cycle 1 day -7 (subjects with run-in)

Study Day (if on or after date of first dose) = assessment date – date of first dose +1

Study Day (if before date of first dose) = assessment date – date of first dose

Cycle Day = assessment date – date of first dose for the cycle +1

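### On-treatment scans run on two unreconciled clocks, nivolumab cycles and calendar weeks, and no rule says which governs when dosing is delayed or nivolumab stops

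*Protocol*

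**What the plan says.** **Infusion clock.** Protocol Section 6.1 gives a nominal length ("The duration of each treatment cycle is 14 days") but adds that "Day 1 or start day of a new cycle is triggered by the infusion of nivolumab"; the Study Evaluation Team may also change the cycle length. The CT row of Table 1 asks for scans "Q5cycles (starting cycle 5) for first 15 months, thereafter Q12 cycles until PD", and Section 3.1 repeats the 5- and 12-cycle intervals. Neither gives on-treatment weeks before the clinical cutoff. After the cutoff, Table 1 sets a floor of one assessment every 26 weeks. Section 10.1 refers sites to Table 1 for the schedule and to Attachment 5 for the detail.

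**Calendar clock.** Attachment 5 has radiology "every 5 cycles (starting Cycle 5) or approximately every 10 weeks up to 15 months after the start of study drug", then every 12 cycles, glossed as about 24 weeks. SAP Section 2.2 says "Each cycle is 14 days, starting from the first dose of study drug", with no infusion trigger. The same SAP section computes cycle day from the first dose in each cycle, and SAP Section 3.4 tabulates cycle delays, so the SAP also treats cycles as able to slip.

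**Where the clocks can part.** Section 6.3 states "A maximum delay of 42 days between doses is allowed". Section 6.4 states "If appropriate and after consultation with the Sponsor, subjects may receive ibrutinib alone", an option that Amendment 7 ended except for subjects rolling over to the extension study.

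**After stopping treatment before progression.** Attachment 5 requires scans every 10 weeks to month 15, then every 24 weeks. Table 1 and Sections 3.1 and 10.1 give six-monthly assessments.

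**The concern.** A scan schedule that moves with dosing makes assessment intensity depend on toxicity. PFS in both documents ends at first documented progression or death, so a postponed scan tends to postpone the recorded event. Part B has no concurrent control and its primary objective is a comparison with historical results, so no second arm shares and cancels the distortion. The SAP censors at the last adequate disease assessment without defining adequate, and it has no rule for late or missed scans. The other question is whether delay can push scans past the cutoff for the primary ORR analysis, which falls 6 months after the last subject's first dose.

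**Working it through.** **1. The plan's own equivalence.** 5 cycles × 14 days = 70 days = 10 weeks, and 12 × 14 = 168 days = 24 weeks. Attachment 5's figures reproduce, but only if every infusion is on time. One 42-day slip between Cycles 5 and 10 makes that scan interval 70 + 42 = 112 days, or 16 weeks, on the infusion clock; it stays 10 weeks on the calendar clock.

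**2. PFS.** If progression falls at random within a scan interval, the mean wait to the next scan is about half the interval: 70/2 = 35 days; 84/2 = 42; 98/2 = 49; 112/2 = 56. A simulation agrees. It used exponential progression times, 200,000 subjects, first scan at day 56 plus the delay, and every later interval 70 days plus the delay; the later 24-week phase was not modelled. The assumed median PFS of 2, 6 or 15 months and the delay per five-cycle block are not in the documents.

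| Delay per block (days) | Mean lag (days), median 2 mo | 6 mo | 15 mo |
|---|---|---|---|
| 0 | 35.5 | 35.1 | 35.0 |
| 14 | 43.5 | 42.3 | 42.1 |
| 28 | 52.2 | 49.9 | 49.3 |
| 42 | 61.2 | 57.6 | 56.5 |

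The 1-year PFS estimate also rises above its on-time value, but not steadily, because it depends on where scans fall around month 12. For a true median of 6 months (true 1-year PFS 0.250) it was 0.279 on time, then 0.294, 0.345 and 0.294. Reported medians likewise jump between scan dates and need not rise with every delay. The upward effect is one on average.

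**3. Duration of response.** Both ends are dated at assessments. Assume response onset uniform over 0.5 to 4 months and median durations of 6 and 15 months. The mean error among detected responders was +7.1 and +5.4 days on time, +4.6 and +1.1 days with 28 days' delay per block, and −6.6 and −8.7 days when one 42-day delay preceded the first scan. The sign is not fixed.

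**4. ORR cutoff.** SAP Section 2.7 sets 1 month = 30.4375 days, so 6 months = 182.6 days. Cohorts B1 and B2 start ibrutinib 7 days before Cycle 1 Day 1. For the last-enrolled subject, in days from first dose:

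| | Cycle 10, Day 1 | Slack | End of Cycle 10 | Slack |
|---|---|---|---|---|
| No run-in | 9 × 14 = 126 | 56.6 | 140 | 42.6 |
| B1/B2 | 126 + 7 = 133 | 49.6 | 147 | 35.6 |

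The Cycle 15 scan (196 to 217 days) misses the cutoff even on time, so two scans are planned before it. The Cycle 10 scan is lost only after 36 to 57 days of cumulative delay, about 5 to 8 weeks (36 to 50 days in B1/B2).

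The 42-day limit can be read as adding 28 days (42 − 14) or 42 days:
- One +28 delay loses nothing.
- One +42 delay loses Cycle 10 only in B1/B2 scanned at cycle end.
- Two maximal delays (+56) lose it in every case except no run-in with a Day 1 scan; two at +84 lose it in every case.
- The Cycle 5 scan, at 56 to 77 days, stays inside the cutoff throughout (77 + 84 = 161).

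Table 8 permits resumption after some events lasting up to 12 weeks from the last nivolumab dose. A 12-week gap adds 84 − 14 = 70 days, more than any slack above. Sections 6.3, 6.4.3 and 11.2 state six-week limits, with exceptions in the last two. Those passages need reconciling before the largest possible delay is known.

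**The case against.** The strongest reply is that a calendar already exists. Section 10.1 points to Attachment 5 for the detail, and Attachment 5 gives 10 and 24 weeks. The SAP counts 14-day cycles from first dose, and delays are capped. Much of this stands, and it rules out several stronger readings:

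- **That scans are counted only in cycles.** Attachment 5 and SAP Section 2.2 say otherwise.
- **That subjects on ibrutinib alone have no scan schedule.** They have no cycle to count under Table 1, but Section 6.1 defines study drug as either or both agents, so Attachment 5's weeks can be applied to them.
- **That duration of response is biased upward.** Late documentation of response offsets late documentation of progression.
- **That delays generally remove scans before the ORR cutoff.** This takes substantial cumulative delay in a late-enrolled subject, and one scan remains.

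The reply does not remove the conflict. Attachment 5 joins the two clocks with an unqualified alternative, its plain 10-week rule covers only subjects who have stopped treatment, and the SAP text defines analysis windows rather than site scheduling. A site following Table 1 literally would move its scans with the infusions.

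**Conclusion.** The documents give two clocks for on-treatment assessment and no rule for choosing between them once infusions are delayed or nivolumab stops. Under the infusion-triggered wording, PFS is biased upward on average: mean detection lag grows by roughly 7 to 26 days for 14 to 42 days of delay in every five-cycle block (42.1 − 35.0 = 7.1 at the low end, 61.2 − 35.5 = 25.7 at the high end). That size rests on assumed delay patterns and progression times; the documents do not say how often infusions slip. The direction for duration of response is not established. The ORR effect is limited to late-enrolled subjects with about 5 to 8 weeks of cumulative delay (about 7 weeks or less in B1/B2), and the sample-size calculation is untouched. The change is worth making but does not threaten the primary endpoint.

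**What to change.** - **Protocol Table 1, Section 3.1 and Attachment 5:** use identical text giving one calendar schedule from first dose of study drug, with the planned 10-week interval to month 15, then 24 weeks, each with a stated window. It should apply regardless of dose delay, interruption or nivolumab discontinuation. Keeping the on-time dates puts the first scan at week 8, or week 9 in B1/B2 (63/7). First dose of study drug is the right origin because PFS starts there. First nivolumab dose would add a 7-day offset in B1/B2 and leave anyone who never receives nivolumab without a schedule.
- **Off-treatment scans:** reconcile Attachment 5's 10-week interval with the six-monthly interval in Table 1 and Sections 3.1 and 10.1.
- **SAP:** define an adequate assessment, and add a rule or PFS sensitivity analysis for late or missed scans (interval-censored PFS would serve). Reporting actual scan intervals by cohort would show how much slippage occurred.

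The cost is mainly wording. The planned number of scans is unchanged, though some will no longer coincide with infusion visits. Amendment 7 says the primary and secondary objectives have already been analysed, so the schedule change helps only remaining subjects. The PFS sensitivity analysis could still go in the study report addendum.
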